14 ADDITIONAL AND SUBGROUP ANALYSES

Primary analysis will be performed separately by sex, age group, baseline CKD stage, baseline iron repletion status ([TSAT ≥20% and ferritin ≥100 ng/mL] vs. others), baseline CRP group (CRP ≤ULN vs. CRP > ULN), eGFR (≤15 vs. >15 mL/min/1.73m²) and other randomization stratification factors, as needed.

In addition, secondary endpoints will be analyzed by subgroups using pooled data from multiple studies, detailed in an Integrated Summary of Efficacy Statistical Analysis Plan.

15 INTERIM ANALYSIS

The study will have no interim analysis with statistical inference. Safety data and dosing decisions will be monitored on an ongoing basis. Ongoing review of safety data will be completed by an independent DSMB.

17 APPENDIX 1: DATA HANDLING CONVENTIONS**17.1 VISIT TIME WINDOWS**

Table 17.1 – 1 below presents the visits assigned for efficacy and safety analyses corresponding to the range of treatment days (window) during which an actual visit may have occurred.

Table 17.1 – 1. Analysis Visit Windows

Analysis Visit	Scheduled Visit Day^a	Window
Baseline, Week 0	Day 1	Days ≤ 1
Week 1	Day 7*(Week #)+1	Days [2, 10]
Week 2	Day 7*(Week #)+1	[Scheduled Day -3, Scheduled Day +6]
Week 4-22	Day 7*(Week #)+1	[Scheduled Day -7, Scheduled Day +6]
Week 24	Day 7*(Week #)+1	[Scheduled Day -7, Scheduled Day +13]
Week 28-xx	Day 7*(Week #)+1	[Scheduled Day -14, Scheduled Day +13]
ET	Earlier Termination, match to a closest scheduled visit in protocol if patient had not been off drug for more than 7 days.	
EoT	Last assessment between Day 2 and EOT visit day, match to a closest scheduled visit in protocol if patient had not been off drug for more than 7 days.	
EoS (FU-4Wk)	Final visit in the Study 15 – 31 days after Last Dose (excluding long term follow-up for early termination).	

^a: Relative to Day 1 (first dose date of study medication)

Table 17.1 – 2. Analysis Visit Windows for HRQoL

CRF Visit	Target Day^a	Analysis Visit Windows Actual Assessment Day	Analysis Visit
Day 1	Day 1	Day 1	Baseline
Week 12	Day 7 * (Week #) + 1	[Target Day – 14, Target Day + 55]	Week 12
Week 28	Day 7 * (Week #) + 1	[Target Day – 56, Target Day + 55]	Week 28
Week 52	Day 7 * (Week #) + 1	[Target Day – 56, Target Day + 83]	Week 52
Week 76	Day 7 * (Week #) + 1	[Target Day – 84, Target Day + 83]	Week 76
EOT Visit		Last assessment between Day 2 and EOT visit day, remapped to the closest next scheduled visit for HRQoL collection.	Week 12, 28, 52, 76 or >1.5 years

^a: Relative to Day 1 (first dose date of study medication)

Analysis Visit windows, as depicted in below, will be used for the Lipid Panel, including LDL cholesterol efficacy study assessment:

Table 17.1 - 3. Analysis Visit Windows for Lipid Panel

CRF Visit	Target Day ^a	Analysis Visit Windows Actual Assessment Day	Analysis Visit
Day 1	Day 1	Day 1	Baseline
Week 4	Day 7 * (Week #) + 1	Day 2 to Day 42	Week 4
Week 8	Day 7 * (Week #) + 1	[Target Day - 14, Target Day + 13]	Week 8
Week 12	Day 7 * (Week #) + 1	[Target Day - 14, Target Day + 27]	Week 12
Week 20,28,36,44,	Day 7 * (Week #) + 1	[Target Day - 28, Target Day + 27]	Week 20,28,36,44
Week 52	Day 7 * (Week #) + 1	[Target Day - 28, Target Day + 41]	Week 52
Q12Wk	Day 7 * (Week #) + 1	[Target Day - 42, Target Day + 41]	Week 64, 72, 88, 100...
ET/EOT Visit		Last assessment between Day 2 and EOT visit day, match to a closest scheduled visit in protocol if patient had not been off drug for more than 7 days	Week xx
EOS (FU-4Wk) Visit		Final visit in the study 15-31 days after Last Dose.	FU-4Wk

^a: Relative to Day 1 (first dose date of study medication)

Visit Day is calculated by (visit date - date of first double-blind study medication + 1). If a patient has ≥ 2 actual visits within the same window, the last visit with non-missing value will be used for analysis.

17.2 REPEATED OR UNSCHEDULED ASSESSMENTS OF SAFETY PARAMETERS

If a patient has repeated assessments prior to the start of double-blind study medication, then the results from the final assessment made prior to the start of study medication will be used as baseline, except where otherwise specified. If post-baseline assessments are repeated or unscheduled, the last post-baseline assessment within a visit window will be used as the study visit assessment for generating summary statistics. However, all post-baseline assessments will be used for PCS value determination and all assessments will be presented in the data listings.

17.3 MISSING DATE OF STUDY MEDICATION

When the last date of double-blind study medication during the study treatment phase is missing, all efforts should be made to obtain the date from the investigator. If it is still missing after all efforts, then the last visit date during the treatment period will be used in the calculation of treatment duration.

17.4 MISSING SEVERITY ASSESSMENT FOR ADVERSE EVENTS

If severity is missing for an AE started prior to the first double blind study medication, then a severity of “Mild” will be assigned. If the severity is missing for an AE started on or after the first double blind study medication dosing, then a severity of “Severe” will be assigned. The imputed values for severity assessment will be used for incidence summary, while the actual missing values will be presented in data listings.

17.5 MISSING RELATIONSHIP TO STUDY DRUG FOR ADVERSE EVENTS

If the relationship to the study medication is missing for an AE started after baseline, a causality of “Related” will be assigned. The imputed values for relationship to double-blind study medication will be used for incidence summary, while the actual values will be presented in data listings.

17.6 MISSING DATE INPUTATION FOR ADVERSE EVENTS

- **Incomplete Start Date**

The following imputation rules apply to the case where the start date is incomplete (i.e., partially missing) for adverse events.

Missing day and month

If the year is same as the year of first day on double-blind study medication, then the day and month of the start date of double-blind study medication will be assigned to the missing fields.

If the year is not the same as the year of first day on double-blind study medication, then January 1 will be assigned to the missing fields.

Missing month only

Treat day as missing and replace both month and day according to the above procedure.

Missing day only

If the month and year are same as the year and month of first day on double-blind study medication, then the start date of double-blind study medication will be assigned to the missing day.

If the month and year are not the same as the year and month of first day on double-blind study medication, then the first day of the month will be assigned to the missing day.

- **Incomplete Stop Date**

If the stop date is complete and the imputed start date as above is after the stop date, the start date will be imputed by the stop date.

If needed, the following imputation rules apply to the case where the end date is incomplete (i.e., partially missing) for adverse events. Other partial end date will not be imputed.

Missing day and month, or Missing month only

December 31 will be assigned to the missing fields.

Missing day only

The last day of the month will be assigned to the missing day.

Table 17.6-1 Imputation of the Analysis Adverse Event Start Date

Reported Date	Date of First Drug Intake	Analysis Date (Derived)
--/MM/YYYY	DD/MM/YYYY	
--/02/2008	14/02/2008	14/02/2008*
--/02/2008	14/02/2007	01/02/2008
--/02/2008	14/02/2009	01/02/2008
--/--/YYYY	DD/MM/YYYY	
--/--/2008	14/02/2008	14/02/2008
--/--/2008	14/02/2007	01/01/2008
--/--/2008	14/02/2009	01/01/2008
DD/--/----		
--/MM/----		No imputation
--/--/----		

Table 17.6-2 Imputation of the Analysis Adverse Event Stop Date

Reported Date	Analysis Date (Derived) *
--/MM/YYYY	31/MM/YYYY or 30/MM/YYYY or 29/MM/YYYY or 28/MM/YYYY
--/--/YYYY	31/12/YYYY
DD/--/----, or --/MM/----, or --/--/----	No imputation

*Death has to be taken into consideration when calculating this.

17.7 MISSING DATE IMPUTATION FOR PRIOR OR CONCOMITANT MEDICATIONS

For prior or concomitant medications, including rescue medications, incomplete (i.e., partially missing) start date and/or stop date will be imputed. When the start date and the stop date are both incomplete for a patient, impute the start date first.

- **Incomplete Start Date**

The following rules will be applied to impute the missing start date. If the stop date is complete and the imputed start date is after the stop date, then the start date will be imputed using the stop date.

Missing day and month

If the year of the incomplete start date is the same as the year of the first dose date of double-blind study medication, then the day and month of the first dose date will be assigned to the missing fields.

If the year of the incomplete start date is not the same as the first dose date of double-blind study medication, then January 1 will be assigned to the missing fields.

Missing month only

Treat day as missing and replace both month and day according to the above procedure.

Missing day only

If the month and year of the incomplete start date are the same as the month and year of the first dose date of double-blind study medication, then the day of the first dose date will be assigned to the missing day.

If the month and year of the incomplete start date are the same as the first dose date of double-blind study medication, then the first day of the month will be assigned to the missing day.

- **Incomplete Stop Date**

The following rules will be applied to impute the missing stop date, if needed. If the last dose date of double-blind study medication is missing, impute it with the last visit date. If the imputed stop date is before the start date (imputed or non-imputed start date), then the imputed stop date will be replaced with the start date.

Missing day and month

If the year of the incomplete stop date is the same as the year of the last dose date of double-blind study medication, then the day and month of the last dose date will be assigned to the missing fields.

If the year of the incomplete stop date is not the same as the year of the last dose date of double-blind study medication, then December 31 will be assigned to the missing fields.

Missing month only

Treat day as missing and replace both month and day according to the above procedure.

Missing day only

If the month and year of the incomplete stop date are the same as the month and year of the last dose date of double-blind study medication, then the day of the last dose date will be assigned to the missing day.

If the month and year of the incomplete stop date are not the same as the month and year of the last dose date of double-blind study medication, then the last day of the month will be assigned to the missing day.

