4 STUDY ENDPOINTS AND ASSESSMENTS

4.1 PRIMARY EFFICACY ENDPOINT

There are two separate regionally-based primary efficacy endpoints in this study depending upon whether the data are being filed to support submission to the US FDA or to Ex-US health authorities, such as the European EMA.

The **primary endpoint for the US (FDA)** submission is defined as the change in Hb from baseline to the average level during the evaluation period (defined as Week 28 until Week 52). Hb values under the influence of rescue therapy will not be censored unless otherwise specified.

The **primary endpoint for the Ex-US** submission is defined as the proportion of subjects who achieve a Hb response at two consecutive visits at least 5 days apart during the first 24 weeks of treatment, without rescue therapy (i.e., blood/RBC transfusion, ESA, or IV iron).

A Hb response is defined, using central laboratory values, as the following:

- Hemoglobin ≥ 11 g/dL and Hb increase from baseline by ≥ 1 g/dL in subjects with baseline Hb > 8 g/dL, or
- An increase in Hb by ≥ 2 g/dL in subjects with baseline Hb ≤ 8.0 g/dL

Both scheduled and unscheduled on-treatment Hb values from the central laboratory will be taken into account.

The first date of the two consecutive visits will be used as the date of response. The second date of the two consecutive visits will be used when evaluating the presence or absence of rescue therapy.

Subjects who discontinued or received rescue therapy before or on the date of the second consecutive Hb value that fulfills the definition of response, will be classified as non-responders.

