12 EFFICACY ANALYSES

Hemoglobin results obtained from the central laboratory will be used for all efficacy analyses.

Baseline Hb is defined as the mean of the last four central laboratory Hb values prior to the first dose of study treatment. Hemoglobin values after a rescue therapy will not be excluded for the US (FDA) submission primary efficacy analysis. Hemoglobin values within 6 weeks after a rescue therapy will be excluded for the Ex-US submission primary efficacy endpoint as well as some sensitivity efficacy analyses.

The **Efficacy Emergent Period** is defined as the evaluation period from the Analysis date of first dose intake up to 7 days after the Last Dose of study drug or EOT Visit, whichever occurs first. This period will be used as reference period for the time to event analyses related to efficacy endpoints, unless specified otherwise.

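### SAP 17.7 gives two conflicting rules for a medication start with a missing day in the first-dose month and no rule for any other month, and rescue medication falls under it

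*SAP*

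**What the plan says.** SAP 17.7 states its scope at the start: "For prior or concomitant medications, including rescue medications, incomplete (i.e., partially missing) start date and/or stop date will be imputed". For a start date that lacks only the day, it gives two branches:

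- **Branch 1.** If month and year equal those of first dose, "then the day of the first dose date will be assigned to the missing day".
- **Branch 2.** The condition is repeated, with a different result: "same as the first dose date of double-blind study medication, then the first day of the month will be assigned to the missing day".

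Nothing covers a start month that differs from the first-dose month.

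The matching adverse-event rule in SAP 17.6 has the opposite condition in its second branch: "If the month and year are not the same as the year and month of first day on double-blind study medication". In 17.7 itself, the second branch of the start-date rule for a missing day and month, and the second branches of both stop-date rules, also turn on the dates being different.

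Rescue dates are used in several analyses. SAP 4.1 makes non-responders of "Subjects who discontinued or received rescue therapy before or on the date of the second consecutive Hb value" that completes the response. SAP 12 excludes Hb within 6 weeks after rescue for the Ex-US primary endpoint and some sensitivity analyses. The efficacy time-to-event window is "defined as the evaluation period from the Analysis date of first dose intake up to 7 days after the Last Dose" or the end-of-treatment visit, whichever comes first.

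**The concern.** Two branches with the same condition and different outputs cannot both be followed, and the case that needs the second branch is left without a rule. A programmer therefore has to choose event dates that the plan was meant to fix in advance.

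This goes beyond a listing convention. SAP Appendix 6 codes ESA, IV iron and blood/RBC transfusion as medications, so 17.7 reaches all three rescue components. Their dates enter:

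- the Ex-US responder classification (SAP 4.1);
- the 6-week Hb exclusions (SAP 12), and the rescue-censoring sensitivity analyses of the US endpoint (SAP 12.2.3);
- the Weeks 28 to 36 secondary endpoints that require no rescue in the preceding 6 weeks or during the period (SAP 12.3, items 1 and 3);
- time to rescue and time to transfusion over 52 weeks, both in the fixed sequence (SAP 12.3, items 6 and 9).

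**Working it through.** No power or sample-size figure is involved. The check is on the logic of the rules.

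**1. Reproduce the plan's own examples.** SAP Table 17.6-1 has three rows with a missing day, all reported as --/02/2008. The 17.6 rule (first-dose date if the month and year match, otherwise the 1st) gives all three printed dates. The same rows were then put through 17.7:

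| First dose | Table 17.6-1 | 17.7 as written | 17.7 with *not* in branch 2 |
|---|---|---|---|
| 14/02/2008 | 14/02/2008 | 14/02/2008 and 01/02/2008 | 14/02/2008 |
| 14/02/2007 | 01/02/2008 | no date | 01/02/2008 |
| 14/02/2009 | 01/02/2008 | no date | 01/02/2008 |

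In the first row the two dates differ by 14 − 1 = 13 days, and the branch 2 date falls before first dose. They agree only if dosing began on the 1st.

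**2. Share of missing-day records in each position.** Assumptions, not in the documents: first dose is equally likely on each of the 365 days of a year, and rescue on each of the first 364 treatment days.

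- Combinations: 365 × 364 = 132,860.
- Rescue in the first-dose month: a month of n days contributes n(n + 1)/2. The sum is 7 × 496 + 4 × 465 + 406 = 5,738, and 5,738 / 132,860 = 4.3%. These have two rules.
- Any other month: (132,860 − 5,738) / 132,860 = 95.7%. These have no rule.
- Among the 5,738, first dose falls on the 1st in 365 cases, where the branches agree. In the other 5,373 (5,373 / 5,738 = 94%), branch 2 would give a date before first dose, while branch 1 still gives the first-dose date.

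These are shares of missing-day records, not of subjects or events.

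**3. After the correction.** Every missing-day record has one date and 17.7 agrees with 17.6. No on-treatment rescue is placed before first dose. The assigned date is at most 31 − 1 = 30 days early, and about 14 days early on average under the same assumption.

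**The case against.** The strongest reply is that this is a dropped word whose intended meaning is plain. The adverse-event rule and the neighbouring rules of 17.7 show what the second branch should say, and 17.7 opens by stating that partial dates will be imputed. That stands, and it limits the point to a correction. It does not supply the missing rule. SAP 11, which compares partial dates on the detail available, does not supply it either: it classifies a drug as prior or concomitant and assigns no date, whereas a Cox model or a 6-week window needs one.

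A reader might infer more than the documents support:

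- **That partly dated rescues are lost.** No section says so, and the SAP 11 example keeps a drug with a missing start day in the first-dose month as concomitant. Such a record would drop out of a time-to-event analysis only if the text were programmed literally.
- **That rescues are moved before first dose.** This needs branch 2 to override branch 1. Even then, the SAP 4.1 non-responder sentence sets no lower bound on the rescue date.
- **That the year-only rule is also an error.** When day and month are missing and the year matches, the start becomes the first-dose date. That can be far too early, but the rule is clear, complete, applied alike to both arms and the same as in 17.6. Replacing it with a midpoint would be a preference.
- **That the effect favours roxadustat.** A false Day 1 rescue changes the Ex-US result only for someone who would otherwise respond. SAP 5.1 assumes 65% responders on roxadustat and 25% on placebo. Suppose 30% of placebo subjects are rescued, and that rescue is independent of response and follows it (assumptions). Then 0.30 × 0.25 = 7.5% of placebo subjects could flip, and roxadustat exceeds this once its rescue rate passes 7.5 / 65 = 11.5%. The documents give no rescue rates.
- **That a handful of placebo events are affected.** With 30% of 400 placebo subjects rescued and 1 to 5% of starts lacking a day, 120 × 0.01 to 120 × 0.05 gives 1.2 to 6 records. Both rates are assumptions and 400 is the enrolment ceiling, so this illustrates scale and is not an estimate.

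**Conclusion.** The missing-day start rule in SAP 17.7 is wrong as written and cannot be carried out: two conflicting dates in the first-dose month (unless dosing began on the 1st), and none in any other month. It covers rescue medication, so it feeds one regional primary endpoint and several endpoints in the fixed sequence. The US primary analysis is not affected, because Hb after rescue is not excluded from it; only its rescue-censoring sensitivity analyses could be.

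The number of affected records is not given and is probably small. The protocol records concomitant medication at each visit (7.1.2) and rescue with its reason in the eCRF (4.6.2), and incomplete data are queried (14.2). The 4.3% and 95.7% shares rest on the uniform-timing assumption. The direction of any bias is undetermined.

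**What to change.** In SAP 17.7, missing day only, start date: insert *not* in the second condition, so that it applies when the month and year of the incomplete start date differ from the month and year of first dose. This matches 17.6 and the stop-date rule. The cost is one word, made before database lock, and no new data.

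Optional, as a sensitivity analysis only: repeat the rescue analyses and the Ex-US responder analysis with the earliest and then the latest possible dates for partially dated rescue records, including year-only records that default to Day 1. This would show whether early dating, up to 30 days for a missing day and longer for year-only records, moves any rescue across a response date or a window boundary. The cost is two re-runs of existing programs.

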11 PRIOR AND CONCOMITANT MEDICATIONS

The World Health Organization Drug Dictionary (WHODD) Version 15 will be used to classify prior and concomitant medications by therapeutic class and preferred term based on ATC code level 3. Prior medication is defined as any medication taken and stopped prior to the first dose of the study medication. Concomitant medication is defined as any medication taken between the day of first dose of the study medication and the day of last study medication date + 28 days, inclusive.

Medication start and end dates will be compared with the start date of study drug and classified as per Table 3. In case of partial or missing dates, comparisons will be made based on the level of details available. For example, if start date of study drug infusion is 04Jan2013, and a medication has a start date of 04Jan2013, the medication will be classified as concomitant. A start date of Jan2013 (i.e., missing day) would also see the medication classified as concomitant.

Table 3. Classification of Prior and Concomitant Medications

Start Date \ End Date	Before start of study drug administration	On or after start of study drug administration	Missing
Before start of study drug administration	Prior	Concomitant	Concomitant
On or after start of study drug administration	Prior	(Treatment Emergent) Concomitant	(Treatment Emergent) Concomitant
Missing	Prior	Concomitant	Concomitant

Both prior and concomitant medication usage will be summarized by the number and proportion of subjects in each treatment group receiving each drug within each therapeutic class using the safety population. Multiple drug usage by a patient will be counted only once.

Detailed analyses may be performed on prior and concomitant medications of special interests such as oral iron, blood pressure medications and lipid medications based on TLF shells.

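### SAP 17.7 can move a medication whose recorded stop month precedes first dose to Day 1, against SAP 11 Table 3, and the SAP does not say which of the two identifies rescue

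*SAP*

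**What the plan says.** SAP 17.7 sets its scope first: "For prior or concomitant medications, including rescue medications, incomplete (i.e., partially missing) start date and/or stop date will be imputed". On order it says: "When the start date and the stop date are both incomplete for a patient, impute the start date first".

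For a start date without its month, the result depends on the year. In the first-dose year, "then the day and month of the first dose date will be assigned to the missing fields"; in any other year, "then January 1 will be assigned to the missing fields". One check can move an imputed start back to the stop date. It applies under this condition: "If the stop date is complete and the imputed start date is after the stop date".

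A stop date that lacks only its day becomes the last day of its month, unless that is the month of last dose. The conflict rule for stop dates is: "If the imputed stop date is before the start date (imputed or non-imputed start date), then the imputed stop date will be replaced" by the start date.

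SAP 11 classifies prior and concomitant medications differently. For partial dates, "comparisons will be made based on the level of details available". Its Table 3 makes any medication that ended before study drug began Prior, whether the start is earlier, later or missing.

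SAP 4.1 classes as an Ex-US non-responder any subject who "received rescue therapy before or on the date of the second consecutive Hb value" that completes the response.

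**The concern.** The two conflict rules in 17.7 work in opposite directions. With a complete stop date, the recorded stop wins and the guessed start moves. With a stop that lacks only its day, the guessed start wins and the recorded stop month is overwritten. Yet a stop month before the first-dose month already proves that the course ended before treatment; the missing day adds nothing to that question.

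The Day 1 date comes from the start imputation. The stop replacement then removes the only recorded evidence against it. SAP 11 reaches the opposite classification for the same record.

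What is at stake depends on which dates are used to find rescue. The Efficacy Emergent Period in SAP 12 opens on the first-dose date, so a Day 1 start lies inside it. If rescue is read from 17.7 dates:

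- response for the Ex-US primary endpoint becomes impossible for that subject (SAP 4.1);
- a Day 1 event enters the 52-week rescue endpoint (SAP 12.3, item 6);
- for a transfusion, a Day 1 event also enters the transfusion endpoint (SAP 12.3, item 9).

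**Working it through.** This is a date rule, so there is no stated figure to reproduce. As a check on the reading, the same start-date logic was applied to the parallel adverse-event examples in SAP Table 17.6-1 and gave all six dated rows there.

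**Rules applied, in the SAP 17.7 order**

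1. Start month missing: first-dose date if the year is the first-dose year, otherwise 1 January.
2. Start day missing, month not the first-dose month: first of the month. (The SAP prints the same condition twice; the second is read as its negation. This does not touch the affected pattern.)
3. Imputed start after a complete stop: start set to the stop.
4. Stop day missing, month not the last-dose month: last day of the month.
5. Imputed stop before the start: stop set to the start.

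**Example, assumed first dose 16/06/2014**

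| Recorded start | Recorded stop | Start after rules 1–3 | Stop after rule 4 | Final stop | Status on imputed dates | SAP 11 Table 3 |
|---|---|---|---|---|---|---|
| --/--/2014 | --/04/2014 | 16/06/2014 | 30/04/2014 | 16/06/2014 | Day 1 | Prior |
| --/--/2014 | 20/04/2014 | 20/04/2014 | complete | 20/04/2014 | Prior | Prior |
| --/02/2014 | --/04/2014 | 01/02/2014 | 30/04/2014 | 30/04/2014 | Prior | Prior |
| --/--/2013 | --/04/2014 | 01/01/2013 | 30/04/2014 | 30/04/2014 | Prior | Prior |

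In the first row the latest possible stop is 31 + 16 = 47 days before first dose, yet the record ends as a Day 1 course. The second row differs only in having the stop day.

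**How specific the pattern is.** All consistent pairs of partial dates from 2012 to 2014 were enumerated for this first-dose date, with a known stop month before June 2014:

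- start month missing, start year 2014: overwritten in 5 of 5;
- start month missing, earlier start year: 0 of 46;
- start month known: 0 of 435.

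These count date patterns. They are not expected frequencies.

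**Which drugs can be affected.** Protocol 4.6.1 includes medications taken within 30 days before screening, and screening lasts up to 6 weeks (Protocol 4.1). The window is at most 6 × 7 + 30 = 72 days before randomization. Against the exclusions in Protocol 5.2:

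- ESA: none within 12 × 7 = 84 days, which is longer than 72, so an eligible subject's last ESA lies outside the window;
- transfusion: none within 8 × 7 = 56 days, leaving about days 56 to 72;
- IV iron: one dose is allowed within 84 days, so it can fall anywhere in the 72.

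**Size, if such records were counted as rescue.** Let q be the affected share, assumed equal in both arms because the therapy precedes treatment, and unrelated to response. The planned rates are 65% and 25% (SAP 5.1). The difference becomes (65 − 25) × (1 − q) points.

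| q (assumed) | Roxadustat | Placebo | Difference | Loss |
|---|---|---|---|---|
| 1% | 64.35% | 24.75% | 39.6 | 0.4 |
| 2% | 63.70% | 24.50% | 39.2 | 0.8 |
| 5% | 61.75% | 23.75% | 38.0 | 2.0 |

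With 300 and 150 subjects, computed power stays above 99.9% in all three rows. In the time-to-rescue analysis, the same share of false Day 1 events in each arm would pull the hazard ratio toward 1.

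**The case against.** The strongest reply is that SAP 11 already settles the matter: it works from the detail recorded, Table 3 makes the record Prior, and 17.7 imputes stop dates only where needed. On that reading a Prior medication never reaches the rescue derivation. This stands in part. A reader might infer that the SAP makes such a record count as rescue, but no passage says so. Equally, no passage says that the SAP 11 class overrides 17.7 dates, and 17.7 names rescue medications. Leaving the stop unimputed would not help either, because the imputed start would still be Day 1.

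The second reply is rarity, and it stands. Three conditions must coincide: start month unknown, start year equal to the first-dose year, and a stop month known and before the first-dose month. A single infusion or transfusion normally has the same start and stop day, so knowing the stop month but not the start month would be unusual. The exclusion criteria also oblige sites to establish when these therapies were given.

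The third reply is that the effect is small and against the drug. That also stands for the responder endpoint: under the assumptions above the difference only shrinks, and power is ample.

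**Conclusion.** The point holds as a narrow defect in a stated rule. For one pattern of partial dates, SAP 17.7 replaces a recorded pre-treatment stop month with Day 1, and SAP 11 Table 3 contradicts the result. The SAP leaves open which dates define rescue.

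Three wider readings are not supported:

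- That every record with two partial dates is affected. With a known start month or an earlier start year nothing is overwritten.
- That past ESA use is a main route. The 84-day exclusion exceeds the 72-day recording window, so such entries should be rare. A single IV iron dose is the realistic case, with a narrow band for transfusion.
- That the US primary result is at risk. SAP 12 keeps Hb values after rescue in that analysis.

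The documents give no frequency, so the responder losses of 0.4 to 2.0 points rest on assumed shares of 1% to 5% and on rescue being read from 17.7 dates. The importance is low. The reason to act is that the Ex-US primary classification of a subject should not turn on whether a stop day was written down.

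**What to change.** Make three changes to SAP 17.7.

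1. Extend the check on the imputed start, for example: *If the stop date is complete, or is partial and its latest possible date is before first dose, an imputed start date later than that date is replaced by it; where that date is before first dose, the medication is Prior.* The first example row then becomes 30/04/2014 to 30/04/2014 and agrees with SAP 11.
2. Keep the existing stop-replacement rule for all other conflicts. Limiting it to complete start dates would create a new error. With last dose 20/03/2015, start --/04/2015 and stop --/--/2015, the imputed start is 01/04/2015 and the imputed stop 20/03/2015, so the stop would precede the start.
3. State that a medication classed as Prior under SAP 11 is not counted as rescue.

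The cost is two sentences of SAP text and a small change to the date-imputation program before database lock. No data collection changes.
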